2.3. Has the research been reviewed before the IRB? No Yes

If yes, please give the date of the review:
and the IRB# (if known):

2.4. Is this research to be performed:

for faculty research No Yes
for a masters thesis No Yes
for a doctoral dissertation No Yes
as part of a course requirement No Yes
as an honors thesis No Yes

Other (explain):

3. Study Rationale

3.1. Using non-technical language, describe the objective of this proposed research including purpose, research question, hypothesis, etc. From your description, the IRB should be able to determine how this proposed study adds to the knowledge on the research topic in order to judge the risks and benefits to the research participants. NOTE: A reference list citing relevant background information must be provided as an appendix with this application.

Childhood apraxia of speech (CAS) is a pediatric speech sound disorder that may lead to persisting speech errors, often despite years of treatment. According to ASHA (2007), CAS is characterized by deficits in the production of accurate and consistent speech sounds, achievement of coordinated transition between speech sounds, and coordination of speech sounds (segmental aspects). Other impairments include difficulty with speech prosody, such as tone, rhythm, pitch and volume changes associated with emotional state and/or context (suprasegmental aspects). There are a variety of characteristics associated with CAS, although the presumed challenge is in planning and programming speech movements (ASHA, 2007; [name], Molfese, et al., 2014). Such impairments may lead to social, academic, and vocational limitations. Thus, there is a need to explore alternate treatment approaches. This study will explore how to improve speech sound production in school-age children with CAS by modifying a standard speech therapy program. Two adaptations to speech therapy will be tested in a 2 x 2 randomized group design.

In Aim 1, we will compare a standard treatment schedule of 2 one-hour sessions per week vs. a treatment sequence beginning with an intensive therapy schedule (10 hrs of treatment in one week), which will then transition to a more distributed practice schedule. This treatment modification is intended to minimize erred practice between training sessions in the early stages of learning, then foster generalization through increased time between practice sessions. Prior studies suggest that distributing speech therapy sessions in a more intense schedule may be beneficial to learning (Namasivayam et al., 2015; Thomas et al., 2014)

In Aim 2, we will compare a standard treatment that includes only verbal feedback to the client during speech practice vs. a treatment sequence that initially includes real-time ultrasound visual feedback of the tongue during speech, which will be faded over the course of treatment. Ultrasound visual feedback is designed to train articulatory movements. It may enhance children's understanding of the articulatory goals of speech

movement patterns by comparing executed tongue movements with intended movements. Prior case reports and single subject experimental designs have shown that speech sound production may be enhanced by including ultrasound visual feedback ([name], Brick & Landi, 2013; [name], [name], McNamara, & Maas, in press), although no prior randomized group studies have been conducted.

All 4 of these treatment conditions (e.g., intensive/distributed, ultrasound visual feedback/no ultrasound visual feedback) have been proven effective in treating childhood apraxia of speech; however, no study to date has compared these treatments to see which treatment (or combination of treatments) is most effective.

Beside these modifications, the other aspects of treatment will be held constant. Outcomes will be evaluated by tracking changes in percent consonants correct from a large speech sample, scored by individuals who are blind to treatment status. The four groups will be compared to determine the extent to which speech sound therapy can be enhanced through a treatment sequence that begins with intensive practice and/or with ultrasound visual feedback.

4. Methods

4.1. Provide a detailed description of what participants will be required to do; including any technical terms or procedures.

All behavioral testing and treatment will take place at the Speech Production Laboratory ([name]).

Evaluation Visit 1 (Baseline 1; ~2 hrs.)

Following consent and assent, the following research procedures will be followed to determine eligibility for the study

1. Hearing screening. ~5 minutes. Quiet beeps are presented through headphones. The child raises their hand if they hear the beep. 25 dB at 500Hz and 20 dB at 1000, 2000, 4000 Hz in each ear. Participants must pass the hearing screening at all frequencies in both ears to be included in the study.
2. Matrix Reasoning subtest of the Wechsler Abbreviated Scale of Intelligence – Second Edition (Wechsler, 2011). ~10 minutes. Child is asked to select the picture (from a set of 5-6) which best completes the pictured pattern. Inclusionary Criteria: t-Score of 37 or better (-1.33 SD from the mean).
3. Goldman-Fristoe Test of Articulation – Third Edition (Goldman & Fristoe, 2015). ~10 minutes. Child is asked to name various pictures which evaluate speech sound production. Inclusionary Criteria: Score less than the 5th percentile.
4. Peabody Picture Vocabulary Test (PPVT-4; Dunn & Dunn, 2007). ~15 minutes. The examiner says a word and the child points to a picture that corresponds to the word, from an array of 4. Complexity of vocabulary increases as children progress through the test. Inclusionary Criteria: Standard Score of 80 or better (-1.33 SD from the mean)
5. Following Directions subtest of the Clinical Evaluation of Language Fundamentals – 5th Edition (CELF-P2; Wiig, Semel & Secord, 2013). ~15 minutes. The examiner gives a direction and the child points to pictures to execute the direction given (e.g., “Point to the black circle that is to the right of the square.”). Complexity of directions increases as children progress through the test. Inclusionary Criteria: Scaled score of 6 or better (-1.33 SD from the mean).

**CAS Criteria: to confirm a diagnosis of CAS, participants must meet CAS criteria on 2 of the 3 tasks described below:*

6. *Maximum Performance Tasks (Rvachew et al., 2005; adapted from Thoonen et al., 1999). ~20 minutes. Maximum length of phonation duration and fricative duration will be collected. Additionally, alternating motion diadochokinetic rates (MRRmono) (e.g., [pʌ pʌ pʌ pʌ pʌ pʌ]) and sequential motion diadochokinetic rates (MRRtri) (i.e., [pʌ tʌ kʌ pʌ tʌ kʌ pʌ tʌ kʌ]) will be collected. CAS Criteria: Apraxia score of 2, Dysarthria score of 0 or 1. Exclusionary criteria: Dysarthria score of 2.
7. *Syllable repetition task (Shriberg et al 2009). ~5 minutes. Children repeat nonsense syllables that contain the sounds /ba ma da na/ ranging from 2-4 syllables in length (e.g.,/daba/ or /mabadana/). Number of items with additions will be recorded. CAS Criteria: 4 or more additions present out of 18 items.

8. *Polysyllabic Naming Task (Murray, McCabe, Heard, et al, 2015; adapted from Gozzard et al, 2004). ~15 minutes. Children will name 80 researcher-selected multisyllabic words presented via pictures on PowerPoint slides (e.g., vegetable, umbrella). Children's productions will be rated for accuracy of lexical stress, percent consonants correct, and number of segregated syllables (e.g., um---brella).

Following the first visit, participants who are eligible will be invited to continue the study. They must agree to be randomized to one of the treatment conditions. If they agree, they will be randomized (through concealed envelopes) to one of four treatment groups, and scheduling will be discussed. The second evaluation visit will be scheduled within one week of the start of treatment.

Evaluation Visit 2 (Baseline 2; ~1.5 hours)

1. 3 subtests comprising the Phonological Awareness Composite of the Comprehensive Test of Phonological Processing – Second Edition (Wagner et al., 2013). ~20 minutes. Subtests include: Elision (e.g., “Say *cowboy*. Now say it again, but don’t say boy.”), Blending Words (e.g., “What word do these sounds make? /m/ --- /u/ --- /n/”), and Sound Isolation (e.g., “what is the second sound in *toast*?”). Subtest scaled scores, percentiles and the Phonological Awareness Composite score, percentile will be obtained.
2. The Recalling Sentences subtest of the Clinical Evaluation of Language Fundamentals – 5th Edition (CELF-P2; Wiig, Semel & Secord, 2013). ~10 minutes. Participants will be asked to repeat sentences of increasing length and complexity immediately after hearing them once. Subtest scaled score will be obtained.
3. Nonword Repetition Task (Dollaghan & Campbell, 1998). ~5 minutes. Participants will be asked to repeat 1 – 4 syllable non-words after the word is presented via computer. Percent consonants correct will be obtained.
4. Structural Oral Mechanism Evaluation. ~5 minutes. The structure and function of oral anatomy will be observed using passive (e.g., observe symmetry of facial structures) and active tasks (e.g., wag tongue from side to side).
5. Multisyllabic Rapid Automatic Naming ([name] & Edwards, 2009). ~5 minutes. Participants will be asked to name a set of 6 randomly-presented multisyllabic pictures across 48 trials. Time of task will be recorded.
6. Multisyllabic Word Repetition Task ([name] & Edwards, 2007). ~10 minutes. Participants will repeat multisyllabic words of 2-5 syllables after the word is presented via computer. Percent consonants correct, percent lexical stress correct, and number of syllable segregations will be obtained.
7. Word Inconsistency Task from the Linguisystems Articulation Test (Bowers & Huisingsh, 2011). ~5 minutes. Participants will repeat multisyllabic words three times after an examiner prompt (e.g., “Say *lifeguard* three times.”) Percent consonants correct, percent lexical stress correct, and number of syllable segregations, and number of different productions will be obtained.
8. Multisyllabic Picture Naming. ~5 minutes. Participants will name 30 researcher-selected multisyllabic words presented via pictures on PowerPoint slides. Percent consonants correct, percent lexical stress correct, and number of syllable segregations will be obtained.
9. Word Inconsistency subtest of Linguisystems Articulation Test (Bowers & Huisingsh, 2011). ~5 minutes. Participants will name 12 multisyllabic pictures 3 times each following an initial model (e.g., “Say *eyelashes* three times”). Productions will be evaluated on whether the 3 trials are consistent (C) or inconsistent (I). Additionally. Percent consonants correct, percent lexical stress correct, and number of syllable segregations will be obtained from the first production of each set.
10. Phrase repetition task. ~10 minutes. Participants will repeat phrases and short sentences containing multisyllabic words after the phrase/sentence is presented via computer (e.g., “factual discussion;” “Renew my newspaper subscription.”). Percent consonants correct, percent lexical stress correct, and number of syllable segregations will be obtained.
11. Three Individual Phrase Probe Lists. ~5 minutes each, 15 minutes total. Based on speech sound errors observed in Baseline 1, specific error patterns will be identified. Individual probes addressing an error pattern will be administered. Participants will read a list of 20 phrases containing the target pattern (e.g., for onset /l/ examples might be: “please go left” and “light the flame”). Percent accuracy will be collected on number of target sounds produced correctly out of 40 using a binary scoring system (i.e., incorrect = 0; correct = 1).

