****The 2 least accurate of the 3 individual phrase probes will be selected as therapy targets.**

Progress monitoring Assessment (~40 minutes): Conducted after 5 weeks, 10 weeks, and 15 weeks.

1. Multisyllabic Word Repetition Task ([name] & Edwards, 2007). ~10 minutes. Participants will repeat multisyllabic words of 2-5 syllables after the word is presented via computer. Percent consonants correct, percent lexical stress correct, and number of syllable segregations will be obtained.
2. Multisyllabic Picture Naming. ~5 minutes. Participants will name 30 researcher-selected multisyllabic words presented via pictures on PowerPoint slides. Percent consonants correct, percent lexical stress correct, and number of syllable segregations will be obtained.
3. Word Inconsistency subtest of Linguisystems Articulation Test (Bowers & Huisinigh, 2011). ~5 minutes. Participants will name 12 multisyllabic pictures 3 times each following an initial model (e.g., "Say *eyelashes* three times). Productions will be evaluated on whether the 3 trials are consistent (C) or inconsistent (I). Additionally. Percent consonants correct, percent lexical stress correct, and number of syllable segregations will be obtained from the first production of each set.
4. Phrase repetition task. ~10 minutes. Participants will repeat phrases and short sentences containing multisyllabic words after the phrase/sentence is presented via computer (e.g., "factual discussion;" "Renew my newspaper subscription."). Percent consonants correct, percent lexical stress correct, and number of syllable segregations will be obtained.
5. Three Individual Phrase Probe Lists. ~5 minutes each, 15 minutes total. Based on speech sound errors observed in Baseline 1, specific error patterns will be identified. Individual probes addressing an error pattern will be administered. Participants will read a list of 20 phrases containing the target pattern (e.g., for onset /l/ examples might be: "please go left" and "light the flame"). Percent accuracy will be collected on number of target sounds produced correctly out of 40 using a binary scoring system (i.e., incorrect = 0; correct = 1).
6. Ultrasound Safety Form (for those receiving US biofeedback). ~5 minutes. Administer a short questionnaire to participant and parent to ensure that procedures and methods continue to be safe and are without adverse effect.

Treatment Design

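### Randomisation comes before Baseline 2, so the structural oral examination, the week-0 phrase probes and the choice of treated sounds all follow allocation

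*Protocol*

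**What the plan says.** Protocol section 4.1 introduces Visit 1 as the visit at which "the following research procedures will be followed to determine eligibility for the study". Its eight listed tasks include neither a structural oral examination nor a phrase probe. After that visit, of the children who qualify and agree, the protocol says "they will be randomized (through concealed envelopes) to one of four treatment groups, and scheduling will be discussed". It adds: "The second evaluation visit will be scheduled within one week of the start of treatment".

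Three things then appear for the first time at Visit 2:

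- Item 4, "Structural Oral Mechanism Evaluation. ~5 minutes". Section 7.7 excludes children with oral-facial structural abnormalities, whether reported by a parent or found on direct evaluation.
- Item 11, the three individual phrase probe lists. On their content: "Based on speech sound errors observed in Baseline 1, specific error patterns will be identified". On their form: "Participants will read a list of 20 phrases containing the target pattern", with 40 target sounds per list, each scored 0 or 1.
- The choice of treated sounds: "The 2 least accurate of the 3 individual phrase probes will be selected as therapy targets".

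The probes are repeated at the progress assessments: "Conducted after 5 weeks, 10 weeks, and 15 weeks". The SAP's outcome is percent target sounds correct on phrase probes. Its primary analysis is the change from pre-treatment to week 10, and week 0 also enters the final model as a covariate.

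On blinding, section 3.1 plans that percent consonants correct from a large speech sample is scored by people blind to treatment. Section 11.2 says blinded outside listeners may hear single words from probe measures.

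**The concern.** Concealed envelopes protect the assignment until they are opened. They do not protect what is measured or decided afterwards. Two consequences follow from the order of visits.

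First, eligibility is not fully settled at randomisation. If the Visit 2 examination shows a structural abnormality, the child is already in an arm. The trial must then either exclude a randomised child or keep one who fails a criterion. The available text gives no rule for this.

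Second, the starting value of the primary comparison and the selection of the two treated sounds are both obtained after allocation. Discussing the schedule tells the family and whoever arranges visits which practice-distribution arm the child is in, because one arm begins with 2 hours a day for 5 days and the other with two one-hour visits a week. If that knowledge reached the person eliciting or scoring the probes, it could shift week 0 in one arm and change which sounds are treated first.

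**Working it through.** The point rests on sequence. The plan states no figure for it, so there is none to reproduce.

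**Order of events (protocol 4.1).** Visit 1 eligibility tasks; then randomisation and discussion of scheduling; then Visit 2 with the oral examination and phrase probes; then choice of two targets; then treatment. The SAP does not name the visit that gives week 0. Visit 2 is the only pre-treatment probe administration described, so equating the two is an inference, but the only one the text supports. The date on which the three candidate patterns are named is not given.

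**Does the visit time allow the examination to move?** Listed minutes:

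- Visit 1: 5 + 10 + 10 + 15 + 15 + 20 + 5 + 15 = 95, against about 120 stated.
- Visit 2: 20 + 10 + 5 + 5 + 5 + 10 + 5 + 5 + 5 + 10 + 15 = 95, against about 90 stated.
- After moving 5 minutes: 95 + 5 = 100 of about 120, and 95 − 5 = 90 of about 90.

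These totals exclude consent and breaks. The move also relieves the visit that is now over its stated length.

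**How would a week-0 scoring shift enter the analysis?** Suppose week 0 is shifted by s points in one arm only.

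- If week 0 is a response, as the SAP's list of time points has it, and also a covariate with one slope b, then with complete data the fitted mean is: mean(group, time) = Ȳ(group, time) − b × X̄(group). In week 10 minus week 0 the b term cancels, so the whole of s enters the contrast.
- If week 0 is only a covariate, b × s enters.

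In neither case does adjusting for the shifted score remove the shift.

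**Unit of measurement.** The SAP does not say how many lists form the outcome. One sound is worth 100/40 = 2.5, 100/80 = 1.25 or 100/120 = 0.83 points for one, two or three lists.

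**Illustration on assumed inputs only.** Take 20 v 20, a two-sided t test with 38 degrees of freedom, SE = SD × √(2/20), and no true effect. The documents give no SD and no shift. For a bias of s points already in the contrast, the rejection rate is:

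| Bias | SD 15 | SD 20 | SD 25 |
|---|---|---|---|
| 1 | 5.5% | 5.3% | 5.2% |
| 2.5 | 8.1% | 6.7% | 6.1% |
| 5 | 17.7% | 12.0% | 9.5% |

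For example, a bias of 2.5 with SD 15 gives SE = 15 × 0.316 = 4.74 and noncentrality 2.5/4.74 = 0.53. The table shows only that small shifts hardly matter and larger ones would; it does not estimate what happens in this trial.

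**The case against.** The strongest reply is that order alone biases nothing. Visit 2 still precedes treatment, so treatment cannot affect it. If the recorded probes are scored blind, the date of the envelope does not affect the scoring. If they are not, weeks 5, 10 and 15 are exposed as well, and opening the envelope later would not cure that. This stands as a limit on the scoring limb.

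A reader might infer that the Baseline 2 probes are scored by someone who knows the arm, or that the false-positive rate really rises to about 18%. The documents support neither. Section 3.1 plans blind outcome scoring, which plausibly reaches week 0 although it names percent consonants correct. Section 11.2 mentions blinded listeners for words from probe measures, though only permissively and for single words. Nothing says that the family or the scheduler scores probes, and scheduling need not reveal the ultrasound arm. Part of the staffing section and the treatment manual were not available, so silence there cannot be counted as a gap. The 18% needs a 5-point shift averaged over a whole arm, the smallest assumed SD, and the full shift entering.

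The route through target selection is also narrow: patterns come from Baseline 1 errors, the lists are read and scored 0 or 1, the two-of-three rule is fixed, and mastered targets are replaced later.

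On eligibility, the Visit 2 examination carries no inclusion or exclusion label, the exclusion also works through parent report, and section 9.6 puts a phone screening before Visit 1. Late exclusions should therefore be uncommon. But it is the only listed direct examination of oral structure, and it comes too late to prevent one.

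**Conclusion.** A cheap improvement to the design, not a demonstrated bias. The order of events is plain in the text: allocation precedes the only listed structural examination, the only pre-treatment phrase probes, and the choice of treated sounds. A child can therefore be found ineligible after randomisation, and baseline measurement takes place when at least the practice-distribution arm can be known. How often the first would happen cannot be derived from the documents; it is probably rare. Bias in week 0 depends on the eliciting or scoring person knowing the arm, which is not shown; the risk is limited and unquantified. The conclusion assumes that week 0 is Baseline 2 and that the direct evaluation in section 7.7 is the Visit 2 oral examination.

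**What to change.** 1. Move the oral mechanism examination to Visit 1, so that eligibility is settled before randomisation. Cost: 5 minutes moved between visits.
2. Open the envelope after the Baseline 2 probes are recorded and the two targets are written down. Cost: less than a week's notice of the schedule, which for some families starts with the five-day intensive week.
3. If that notice is too short, record and date the three error patterns before opening the envelope, and have the recorded Baseline 2 probes scored blind to arm for both target selection and week 0. Cost: prompt scoring of 3 × 40 = 120 sounds per child, for about 15 children a year (section 6.5), from audio that section 11.7 already requires. Someone blind to allocation must be named for this. It closes the scoring route but not elicitation, which the read lists already constrain.

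Some of the SAP's wording is in the past tense, so enrolment may be over. In that case, disclose that allocation preceded baseline probing and target selection, and confirm that the phrase probes were scored blind to arm at every time point. If they were not, rescore from the audio: 40 × 120 = 4,800 sounds for week 0 alone, or up to 4 × 4,800 = 19,200 for all four time points mixed (12,800 or 6,400 if the outcome uses two lists or one). Mixing is needed if scorers are also to be blind to time point. Rescoring cannot undo target selection. None of this needs a new visit or procedure.

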****The 2 least accurate of the 3 individual phrase probes will be selected as therapy targets.**

Progress monitoring Assessment (~40 minutes): Conducted after 5 weeks, 10 weeks, and 15 weeks.

1. Multisyllabic Word Repetition Task ([name] & Edwards, 2007). ~10 minutes. Participants will repeat multisyllabic words of 2-5 syllables after the word is presented via computer. Percent consonants correct, percent lexical stress correct, and number of syllable segregations will be obtained.
2. Multisyllabic Picture Naming. ~5 minutes. Participants will name 30 researcher-selected multisyllabic words presented via pictures on PowerPoint slides. Percent consonants correct, percent lexical stress correct, and number of syllable segregations will be obtained.
3. Word Inconsistency subtest of Linguisystems Articulation Test (Bowers & Huisinigh, 2011). ~5 minutes. Participants will name 12 multisyllabic pictures 3 times each following an initial model (e.g., "Say *eyelashes* three times). Productions will be evaluated on whether the 3 trials are consistent (C) or inconsistent (I). Additionally. Percent consonants correct, percent lexical stress correct, and number of syllable segregations will be obtained from the first production of each set.
4. Phrase repetition task. ~10 minutes. Participants will repeat phrases and short sentences containing multisyllabic words after the phrase/sentence is presented via computer (e.g., "factual discussion;" "Renew my newspaper subscription."). Percent consonants correct, percent lexical stress correct, and number of syllable segregations will be obtained.
5. Three Individual Phrase Probe Lists. ~5 minutes each, 15 minutes total. Based on speech sound errors observed in Baseline 1, specific error patterns will be identified. Individual probes addressing an error pattern will be administered. Participants will read a list of 20 phrases containing the target pattern (e.g., for onset /l/ examples might be: "please go left" and "light the flame"). Percent accuracy will be collected on number of target sounds produced correctly out of 40 using a binary scoring system (i.e., incorrect = 0; correct = 1).
6. Ultrasound Safety Form (for those receiving US biofeedback). ~5 minutes. Administer a short questionnaire to participant and parent to ensure that procedures and methods continue to be safe and are without adverse effect.

Treatment Design

Aim 1: In addition to the above assessment visits, participants will be randomized to one of four treatment conditions.

Table 1: Four groups to which children will be randomized in a 2 x 2 Factorial design

Distribution Conditions	Biofeedback Conditions	
	Sequenced Biofeedback (Biofeedback → No biofeedback)	No biofeedback
Sequenced Distribution (massed→distributed)	n=10	n=10
Distributed Practice	n=10	n=10

We will randomize children with CAS to one of four groups. We will test generalization effects in a x 2 (Mass→Distributed vs. Distributed only Practice Schedule) x 2 (Sequenced Biofeedback→No biofeedback vs. No biofeedback) factorial treatment design.

Participants will be randomly assigned to either Distributed Practice or Sequenced Distribution (massed→distributed practice). In both conditions, the cumulative treatment dose will be 20 hours of treatment. Half of our participants (n=20) will receive treatment following a distributed model of twice per week for 60 minutes for 10 weeks, for a total of 20 hrs of therapy. The remaining participants (n=20) will receive treatment following a sequenced approach of massed then distributed practice, with 10 hrs occurring in the first week (2 hrs per day for 5 days, with a 10 minute break in between sessions each day), then 3 one-hour sessions per week for 2 weeks, and finally 2 one-hour sessions per week for 2 weeks.

Table 2: Overview of Aim 1 Schedule by Group: Operationalized Definitions

	Wk 1	Wk 2	Wk 3	Wk 4	Wk 5	Wk 6	Wk 7	Wk 8	Wk 9	Wk 10	Wk 15
Distributed Practice Group (n=20)	1 hr x 2 visits & Assess	1 hr x 2 visits & Assess	Assess								
Sequenced Distribution Group (n=20)	2 hr x 5 visits	1 hr x 3 visits	1 hr x 3 visits	1 hr x 2 visits	1 hr x 2 visits & Assess	-	-	-	-	Assess	Assess

Aim 2: In addition to the above randomization based on schedule, half of the participants (n=20) will be randomized to receive treatment without ultrasound visual feedback and half (n=20) will be randomized to receive treated with ultrasound. The practice structure described above (see *Overview of Treatment Procedures*) will be identical, and the difference between conditions therefore will be whether or not the clinician and client have access to a visual referent during speech production to describe aspects of both erred and correct tongue movements.

In the Sequenced Biofeedback → No biofeedback condition, participants begin treatment such that ~50% of the session includes ultrasound feedback of the tongue. Each session will be divided into four 13 minute Time Periods (A, B, C, D). The ultrasound will be available for practice in Time Periods A and C, whereas practice will continue without ultrasound for periods B and D. When the ultrasound is used in Time Periods A and C, it will be available only when the participant is practicing at treatment Levels 1 (syllables), 2 (monosyllabic words), 3 (multisyllabic words) and 4 (phrases). However, after 8 hrs of treatment, *ultrasound use will be faded* such that it is only available as children are at practice Levels 1 and 2 to encourage independent practice without visual support at more complex levels. During the final 4 hours of treatment, no visual feedback will be available.

[figure not shown]
Table 3: Structure for a 60-min Session: Operationalized Comparison of Ultrasound use for Aim 2

Sequenced Biofeedback → No Biofeedback Group (n=20)				
Time Period:	A	B	C	D
Treatment target	Target 1	Target 1	Target 2	Target 2
Ultrasound available: First 8 hrs of therapy	Used on Levels 1: Syllables 2: Monosyllabic words 3: Multisyllabic words 4: Phrases	None	Used on Levels 1: Syllables 2: Monosyllabic words 3: Multisyllabic words 4: Phrases	None
Next 8 hrs of therapy	Used on Levels 1: Syllables 2: Monosyllabic words	None	Used on Levels 1: Syllables, 2: Monosyllabic words	None
Last 4 hrs of therapy	None	None	None	None
No Biofeedback Group (n=20)				
Time Period:	A	B	C	D
Treatment target	Target 1	Target 1	Target 2	Target 2
Ultrasound use	None	None	None	None

When biofeedback is required, we will use an EchoBlaster 128 ultrasound with PV 6.5 probe to provide real-time visual display of the tongue. When it is available, *all verbal feedback* by the clinician will be expected to reference the visual display. For example, when treating /-ks/ sequences, feedback can be provided to the client about elevation of the tongue body and lowering of the tongue tip for /k/, followed by elevation of the tongue tip/blade for /s/. The participant's attention will therefore be drawn to these movements on the screen and participants will be instructed to visually monitor their speech movements and make corrections based on the visual feedback. As an example, **Figure 2** shows ultrasound images for /r/ (anterior is right, posterior left). The distorted /r/ (top) has a low tongue tip/blade (right side of the image) and high tongue body, whereas the correct /r/ (bottom) has a high tongue tip/blade and a lowered tongue body.

When no biofeedback is required, practice will be similar to traditional speech therapy.

Feedback will be based on the clinician's percept of the child's production unaided by technology. However, the practice and feedback structure will still follow that which is outlined in Table 3.

Overview of Treatment Session Procedures

A manual is posted on our website outlining practice procedures (speechproductionlab.syr.edu). The general structure involves a pre-practice stage and a practice stage in each session. During **pre-practice**, target sound sequences (e.g., /lo-/) are elicited through frequent phonetic cues, shaping strategies, and verbal descriptions of articulation. When biofeedback is available, and visualization of is used to encourage the child to modify shape and position and to properly sequence movements for acceptable productions. A pre-established criterion (i.e., 12 correct productions of the target) must be met to progress from the pre-practice stage to the practice stage. For clients with significant difficulty producing the target sound sequences, pre-practice may take the majority of a session (during the early stages of therapy); for clients who have developed the ability to successfully perform the task (during the later stages of therapy), pre-practice may be completed in 1-2 minutes.

During the **practice** stage, there are multiple levels of practice with target stimuli that are chained. Chains involve a target sound sequence (e.g., /lo-/) produced first in syllables then in more complex environments. Each practice level involves 6 blocked attempts at the target. If at least 5 of 6 productions are correct, practice continues on the same chain the next highest level; if fewer than 5 are correct, practice returns to the Level 1 on a different target (e.g., /kl-/). The first practice level is at the syllable level, followed by monosyllabic words, multisyllabic words, phrases, and sentences. For each sound sequence that is targeted, 8 chains will be used for treatment in each session. The table below outlines the practice parameters.

Table 3: Practice Stage: Operationalized Parameters for Blocks of 6 Attempts (all sessions)

Practice Level	Level 1	Level 2	Level 3	Level 4	Level 5
Targets	Syllables	Monosyllabic word	Multisyllabic word	Set phrase	Client-generated sentence
Example chain	/lo/	Load	Loading	Loading the truck	[Loading in sentence]

Each hour of therapy will address two different sound targets, with the first half of the session addressing one sound target and the second half addressing another; the order will be counterbalanced each session. Targets are selected as a phoneme in a syllable position, and four exemplars are selected for that sound target. For example, /l/ in onset could be addressed with sound sequences such as /li-/, /lo-/, /kl-/, /pl-/ during the first half hour, and /k/ in coda could be treated with sound sequences such as /-ɪk/, /-ʊk/, /-ks/, /-sk/ during the second half hour. Targets will be selected based on the lowest percent accuracy before treatment based on the sound-specific Probes. Two targets will be treated per session; however, new targets will replace previous targets if the participant successfully completes Level 5 for 2 chains during 2 consecutive sessions.

The above components of treatment are held constant, allowing for manipulation of other parameters (distribution of sessions for Aim 1 and exposure to visual feedback for Aim 2). These standard components to treatment, as well as the manipulated components for Aim 1 and 2, will be monitored and reported for treatment fidelity and to ensure replicability.

4.2. Describe how you will have sufficient time to conduct and complete the research?

The grant provides one course release per year for [name], along with summer salary. The grant also covers 50% of [name] time as well as paid time for research assistants. We will devote time for weekly lab meetings with research assistants throughout the year to ensure the progress progresses.

4.3. Surveys, interviews, questionnaires will be conducted:

No (Skip to 4.4)
 Yes Include all research instruments including surveys, questionnaires, sample interview questions, etc. as separate appendices. If the survey instrument is commonly used in your discipline, only provide a citation to the instrument.

4.4. Community Based Participatory Research (CBPR) is described as research that is conducted as an equal partnership between traditionally trained "experts" and members of a community. Is this research categorized as CBPR?

No. (Skip to 4.5)

Yes. Please explain:

4.4.1. In CBPR research studies, the community participates fully in all aspects of the research process including conception, design, and analysis.

With this in mind, describe how you plan to engage community members in your research study:

4.4.2. Describe how you plan to provide community members with appropriate training for human subjects research? Include in your description what training will be provided.

4.4.3. Describe your plan to disseminate research findings with members of the community throughout the course of your study.

